Power. This is a pilot study aimed at evaluating feasibility, and as such, sample size was not determined by power. Nevertheless, we provide an estimate of an effect size that we may be able to detect with a conservative estimate of roughly 2 enrolled participants per clinic month, or 50 participants in CT and 80 participants in TES. As power calculations for delayed roll-out trials would involve speculation of both between period and within period autocorrelations, which would be speculative at this point, we estimated an effect size for a cluster randomized trial, with estimated ICC of 0.01 within clinic. Based on this sample size, we will have 80% power to detect an effect size of 0.62 in an intent-to-treat analysis. This equates to a difference in PHQ-9 scores between CT and TES after treatment of 3.1 assuming a SD of 5.

Implementation (Sub-Aim 2.2).

We will examine the implementation outcomes: reach and cost. Reach is defined as the implementation cascade including 1) the number of eligible patients (PHQ-9 \geq 10 at clinic visit during recruitment period); 2) number of patients consented and randomized; and 3) number of patients completed (6 or more weeks in treatment). As is common in implementation research, we will likely be underpowered for standard statistics;^{102,107} we will therefore examine implementation metrics (adoption, and reach) using control charts and run charts over time, as well as charts centered on the time when clinics are transitioned from CT to TES.^{108,109} These charts plot observed rates or means together with ± 1 & 2 SDs and then plot the measures monthly to determine if there is significant trend or change in implementation metrics over time. To evaluate time to stable implementation in the TES arm, we will use run charts examining runs, shifts, and trends to look for nonrandom variation that indicates actual change or stability of the implementation metrics over time.¹¹⁰ Cost for a depression free day (DFD), with DFD estimated using linear interpolation of PHQ-9 scores using a criterion of PHQ-9 $<$ 10 and compared across conditions using both a t-test (on cost) and incremental cost effectiveness ratio (ICER) analysis.¹¹¹⁻¹¹³ This metric allows comparison with other studies.^{114,115}

D6.3 Aim 3. Experimental Therapeutics. We will evaluate if the core UCD targets (usability, usefulness, and satisfaction) in the TES will result in increased objective and subjective markers

STU#:00211887

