of engagement relative to the CT, with by testing the mediational effects of subjective and objective engagement with the apps on the primary outcomes, depression (PHQ-9) and anxiety (GAD-7). Subjective engagement will be measured using the Twente Engagement with eHealth Technologies Scale (TWEETS), while objective engagement will be measured by app use (number of app launches and time from first to last use). We hypothesize that the difference between the TES and CT will be mediated by subjective and objective engagement. We also hypothesize the moderating effects of patient characteristics on subjective and objective engagement, depression, and anxiety will be lower in the TES arm, relative to CT, as a result of inclusion of users' voices through the design processes used in the creation of the TES app.

Mediation will be tested using methods by Iacobucci.¹²¹ Using analogous adaptations of methods to Preacher's methods,^{122,123} we will be able to test for moderation and mediation together. Between patient characteristics and actionable targets (subjective and objective use) we could test many moderated mediation (conditional indirect effects) which may indicate that a particular subset of participants (defined by subjective or objective use, and patient characteristics) may be more likely to benefit from TES. Multiple models will need to be fit, increasing the possibility of an inflated type I error. To prevent this, we will implement a false discover rate (FDR) control using methods by Benjamini-Hochberg¹²⁴ although as these are pilot studies, we will test these models at a FDR of 10%. Depending on the distribution of the variables under consideration, we will fit linear or logistic regression models to estimate regression parameters a (TES and the relationship to potential mediators) and b (mediator relationship to the outcome). Iacobucci shows that a normally distributed test statistic can be constructed from standardized regression parameters $Z_a = a/SE_a$ such that $Z(\text{mediation}) = Z_a * Z_b / (\sqrt{Z_a^2 + Z_b^2 + 1})$ can be used to test for mediation. Further, we can examine if there is further moderation of these models such that any patient covariate could moderate the relationship between TES use and depression outcomes. Power analyses for the individual RPs can be found in the RPs.

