Power. While sample size and power calculations for mediational analyses are subject to speculation, Fritz and MacKinnon¹¹⁶ show that our effective sample size of 112 (130 divided by the design effect determined by the number of patients per clinic and ICC within clinic) achieves 80% power to detect between a medium effect size, and small-medium effect size for the a and b paths (medium ES = 0.39, small-medium ES=0.26) using the joint tests we propose.

SMS Data and Focus Group Analysis Plan

Data from SMS records and focus groups will be analyzed qualitatively via thematic analysis as described by Braun and Clarke or via semi-open iterative coding. Semi-open iterative coding would allow us to begin with a set of codes relevant for the trial and stay open to new codes (as in thematic analysis).

Organizational Level Data

Rush University Medical Center personnel will provide aggregated data on TES Reach/Adoption on a routine basis. The Rush team will ensure a de-identified DUA is in place and will work with the Research Core to have the data extracted and de-identified prior to the transfer. Additionally, the request will be reviewed and approved by the Rush Data Governance Committee. These de identified data exports may include the following information which will enable the study team to understand what proportion of patients who screened positive for depression and/or anxiety were offered participation in the trial and engaged in TES. For patients in each participating clinic:

- Number of patients screening positive on PHQ-9, GAD
- Number of patients being referred to study

PROVISIONS TO MONITOR THE DATA TO ENSURE THE SAFETY OF PARTICIPANTS

STU#:00211887

CLINICAL TRIAL

Oversight of the trial is provided by the Principal Investigators, Drs. [name], [name], and [name]. The NU research coordinator, [name] will ensure that informed consent is obtained prior to engaging in research activities, and that the study is conducted according to the IRB-approved research plan.

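### The Aim 3 mediation statistic is not normally distributed as the protocol states; the test is conservative for weak to moderate paths, and the quoted 80% power belongs to a different test

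*Protocol*

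**What the plan says.** The mediation analysis is specified only in the Protocol, Data Analysis, D6.3 Aim 3. Linear or logistic regressions give path a (TES to mediator) and path b (mediator to outcome), each divided by its standard error. The protocol then says that "a normally distributed test statistic can be constructed from standardized regression parameters", namely Za·Zb/√(Za²+Zb²+1). It names no bootstrap, distribution-of-product or other reference. For multiplicity it applies Benjamini-Hochberg and says "we will test these models at a FDR of 10" per cent, giving no per-test level.

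The Power paragraph that follows says that "our effective sample size of 112" (130 divided by a design effect) "achieves 80% power to detect between a medium effect size, and small-medium effect size for the a and b paths", with "medium ES = 0.39, small-medium ES=0.26", "using the joint tests we propose". The D6.3 text describes no joint-significance test. The SAP contains no mediation analysis.

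**The concern.** A product of two estimates, even when scaled, is not normal when one or both true paths are zero, and that is the null hypothesis of no mediation. If the statistic is narrower than a standard normal under that null, p-values read from the normal table are too large, and these p-values go into the false discovery rate step. Mediation of the TES effect by engagement is a stated Aim 3 hypothesis, and with 130 patients there is little power to give away. The power paragraph also appears to describe a test other than the one specified, so a reader could take 80% as the power of the planned analysis.

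**Working it through.** **Inputs.** Effective N = 112 and path sizes 0.26 and 0.39 come from the Aim 3 Power paragraph. The statistic comes from D6.3. Three assumptions are added. The per-test level is two-sided 5% (c = 1.96), with other levels shown below. Za and Zb are independent with unit variance and means a√N and b√N. Path sizes are standardised, so √112 = 10.583 gives expected Z of 0.26 × 10.583 = 2.75 and 0.39 × 10.583 = 4.13.

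**The plan's own figures.** The design effect is 130/112 = 1.161. With the "estimated ICC of 0.01 within clinic" of the effectiveness power paragraph, this implies 1 + 0.161/0.01 ≈ 17 patients per clinic. Joint-test power is P(|Za|>1.96) × P(|Zb|>1.96). With P(Z > 1.96 − 2.75) = 0.786 and P(Z > 1.96 − 4.13) = 0.985:
- 0.26/0.26: 0.786² = 61.7%
- 0.26/0.39: 0.786 × 0.985 = 77.4%
- 0.39/0.39: 0.985² = 97.0%

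The joint test reaches 80% at a = b = 0.303, which lies between 0.26 and 0.39. The stated 80% therefore reproduces, for a joint test.

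**Planned statistic under no mediation (N = 112).**

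| True paths | SD (should be 1) | Type I error, planned | Type I error, joint |
|---|---|---|---|
| 0 / 0 | 0.43 | 0.006% | 0.25% |
| 0.26 / 0 | 0.80 | 0.7% | 3.9% |
| 0.39 / 0 | 0.89 | 2.0% | 4.9% |

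The planned test nears its nominal level only when one path is very strong: 4.4% at an expected Z of 10.

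**Why it is always stricter than the joint test.** Since √(Za²+Zb²+1) exceeds the larger of |Za| and |Zb|, the statistic is always smaller in size than the smaller of the two. Its p-value is therefore always larger than the joint-test p-value (the larger of the two path p-values). This holds at any cut-off and for linear or logistic models.

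**Size of the loss.** For a given Za with |Za| > c, the planned test rejects when |Zb| > c·√((Za²+1)/(Za²−c²)). Integrating this over Za at N = 112, 5% level:

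| Paths | Planned | Joint | Loss (points) |
|---|---|---|---|
| 0.26 / 0.26 | 34.5% | 61.7% | 27 |
| 0.26 / 0.39 | 62.2% | 77.4% | 15 |
| 0.39 / 0.39 | 92.3% | 97.0% | 5 |

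A Monte Carlo distribution-of-product interval gives 59.3%, 77.7% and 96.8%, close to the joint test. Regression simulation at 0.26/0.26 gives 33.6% against 58.9%. At a = b = 0.303, where the joint test has 80%, the planned test has 58.7%.

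**Other per-test levels.** At 10% the three losses are 19, 7 and 1 points. The largest loss over all path sizes is 22.6 points at 10%, 27.4 at 5%, 33.2 at 2% and 37.2 at 1%. For 0.26/0.26 the loss is 30 points at 2% (14.3% v 44.2%) but 26 at 1% (6.2% v 32.5%), because by then both tests have little power left.

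**A worked case.** With Za = Zb = 2.8 (p = 0.005 each), the statistic is 7.84/√(15.68+1) = 1.92, p = 0.055. Solving z²/√(2z²+1) = 1.96 gives z = 2.86, so two equal paths must each reach p = 0.0043.

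**The case against.** The strongest reply is that the plan sets no 5% level. Under a 10% false discovery rate, p = 0.055 can be rejected, depending on its rank among the models. The worked case therefore does not show that two clearly significant paths must fail, although a reader might infer that. This stands, and it is why the 5% level is marked as an assumption. It does not remove the problem: the planned p-value exceeds the joint-test p-value at every cut-off, and Benjamini-Hochberg can demand cut-offs stricter than 5%.

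A second reply is that the 27-point loss is the weak-path end. The protocol's target lies between 0.26 and 0.39, and with both paths at 0.39 the loss at the 5% level is 5 points. This also stands. It would be too much to say that the test is far too conservative throughout, or that a null mediation result would usually be an artefact.

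Third, the very low error rate with both paths zero is not peculiar to this statistic. The joint test has 0.25% there and the Monte Carlo interval is similarly low. The more telling comparison is with one path zero.

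Fourth, a joint test may be what was meant, as the power paragraph suggests. If so, the loss would not arise, but D6.3 would still specify a different statistic and reference distribution.

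Finally, the power figures rest on linear models, while the plan also allows logistic models and one mediator is a launch count. The direction of the error carries over; the exact sizes may not.

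**Conclusion.** The statement of normality is wrong as written. The approximation is poor when paths are weak to moderate and adequate only when one path is very strong. At effective N = 112 and an assumed two-sided 5% level, the loss against a joint-significance test is 27, 15 and 5 points for the three path pairs that the protocol's effect sizes form. It is smaller at a 10% level and generally larger at stricter ones. The sizes assume standardised paths and linear models. If path a is read instead as a raw difference between arms in SD units, with "50 participants in CT and 80 participants in TES", power is lower throughout, but the largest loss is similar, at about 25 points.

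A reader might infer that the 80% power figure is miscalculated. The documents do not support that: it reproduces for a joint test at path sizes within the stated range. The fault is that it is attached to a different test. Nor does the point touch the PHQ-9 and GAD-7 effectiveness comparison or raise the risk of false positives. The cost is missed mediation in a pilot analysis, and the correction should be made because it is cheap.

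**What to change.** Change the Protocol, D6.3 Aim 3 and its Power paragraph. The SAP needs no correction here, since it has no mediation analysis.

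- Delete the statement that the statistic is normally distributed.
- Test the indirect effect a·b, from the same two regressions, by either a percentile-bootstrap or Monte Carlo (distribution-of-product) interval and p-value, or the joint-significance test that the Power paragraph already cites, taking the larger of the two path p-values. The joint test is the smaller change.
- Pass those p-values to the existing Benjamini-Hochberg step.
- Name the test to which the 80% power refers, with its path sizes and per-test level.

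The cost is a few lines of code and a short protocol edit, with no new data. In simulations at n = 130, type I error for the Monte Carlo interval ran from 0.2% to 5.8%, with simulation error of about 0.4 points, so it stayed near or below nominal.

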Additional data will be collected to evaluate intervention use, usability, satisfaction, and engagement. Measures of discrimination and stigma will be administered. Patient self-report measures have been uploaded to the eirb+ system for review. See data collection packets containing the measures to be administered via REDCap at screening, baseline, week 4, week 8, and week 12.

Assessment Strategy for Sub-aim 2.2 Implementation

Reach will be measured as follows: 1) Number of eligible patients will be the number of patients with PHQ-9 \geq 10 at a clinic visit during the study recruitment period; Treatment uptake will be the number of patients consented and randomized; 3) Treatment completion will be the number of patients completing at least 6 weeks of the 8-week treatment.

STU#:00211887

Optional Usability/User-Feedback Interviews (4w, 6w, 8w)

Participants will be informed during the informed consent process that they may be invited to complete optional interviews. All interviews will be conducted by telephone. At the end of the week 4 self-report survey, participants will be asked if they would like to provide additional feedback about their experience using the Vira app and working with the study coach via paid interviews. Participants who express interest in providing feedback will be contacted by study staff to schedule the optional interview session(s). More information about the nature and timing of the optional interviews is provided below.

Vira app usability interviews (4w, 6w, 8w)

As we begin enrolling the clinical trial, we will invite the first participants randomized to the TES condition to provide feedback on the usefulness and usability of the Vira application. These optional interviews will be administered to approximately 10 participants.

The app usability interview guide has been uploaded to the eirb+ portal for review.

Coaching user feedback interviews (4w)

All participants randomized to the TES will be invited to share additional user feedback about their experience working with the study coach at the week 4 (mid-treatment) timepoint.

The coaching user feedback interview guide has been uploaded to the eirb+ portal for review.

Failure to Initiate Treatment

If a participant fails to initiate treatment or fails to continue with treatment but is still engaged with the study, a single question survey will be administered to gauge the reason why they decided to not engage with the treatment.

Optional Focus Group (Post-Trial)

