RCT Timeline of Participant Activities

Active participation will last 12 weeks for each study participant. Participants will use the study apps and receive coaching (group 1 only) for the first 8 weeks. We will unobtrusively track all communication with the study coach. Assessment will continue through week 12. Study assessment milestones are laid out in tables 3 and 4 below.

Table 2. Online surveys to be administered to all participants

Method	Week 0	Week 4 Mid-Treatment	Week 8 End of Treatment	Week 12 Post-Treatment
Self-report Survey	x	x	x	x
App Usage	Continuous, unobtrusive			

Table 3. Optional interview data to be collected from patients randomized to TES

Method	Week 4 Mid-Treatment	Week 6	Week 8 End of Treatment
Vira app usability interview	x	x	x
Coaching user-feedback interview	x		

Table 4. Optional focus group be completed with patients randomized to control and TES

Method	Post-Trial Completion
Focus Group (semi-structured interview guide)	x

The anticipated completion date for primary analyses is March 31st, 2024.

RCT INCLUSION AND EXCLUSION CRITERIA:

Trial participation will be offered to patients at Rush University Medical Center aged 13 or older. Children under the age of 13 will be excluded given likely differences in development and

STU#:00211887

smartphone ownership that would make such young children an inappropriate population for evaluating the technology enabled service and implementation plan.

Inclusion Criteria: US Citizen/Resident (for payment purposes) living in the US during the 12-week study period (for tech functionality, data security, and safety management purposes), 13 years or older (if age 13-17, parent/caregiver must provide consent, a consent process is in place for English-speaking minors with Spanish-speaking parents), English speaking, eligible to receive care through Rush University Medical Center or its clinical affiliates, owns an Android or iPhone smartphone with an up-to-date operating system, has used a smartphone in the last 7 days, at least moderate symptoms of depression (PHQ-9 greater than or equal to 10) and/or anxiety (GAD-7 greater than or equal to 8)

Exclusion Criteria: Severe suicidality (as defined by presence of a plan + intent to act on that plan)

VULNERABLE POPULATIONS

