There are a number of pathways through which suicidal risk can be detected. During the trial phases, suicidality may be detected through automated PHQ-9 self-report assessments, through direct communications with the study coach via phone or messaging (email, text, etc.) or through direct communication with research staff during user feedback interviews. In each of these instances, the goal will be to rapidly acquire additional information that can trigger safety procedures if necessary.

Suicidality will be monitored through weekly assessments. Participants who rate Question 9 of the Patient Health Questionnaire-9 (i.e., "Over the last 2 weeks, how often have you been bothered by thoughts that you would be better off dead or of hurting yourself in some way") a 1 or higher will receive a second item from the Beck Depression Inventory (2nd ed.) that is more specific in identifying suicidal intent, asking participants who indicate that they would like to kill themselves, or would kill themselves if they had the chance will be considered to have "elevated suicidality." For participants with "elevated suicidality," a crisis message is displayed to the participant (see message verbiage below) and an alert is sent to the research team and a trained member of the research team will respond within two business days by calling the patient to enact the assessment procedures based on the Columbia Suicide Severity Rating Scale and management procedures that follow clinical guidelines described below.

Crisis Message Displayed to Participants in REDCap:

This research study is NOT an emergency or crisis service.

If you are experiencing a life-threatening emergency such as serious thoughts or plans to end your own life or the life of anyone else, please call or text the numbers 9-8-8 to reach the Suicide and Crisis Lifeline.

If you're looking for crisis supports who specialize in serving members of the LGBTQIA+ youth communities, please call the Trevor Project at [name] or text "START" to [name]

For non-crisis support, warmlines are also available, find one here:

<http://www.mhanational.org/warmlines>

When suicidality is expressed by the participant directly to the study coach in a phone call or text, the coach similarly follows up to conduct a risk assessment based on the Columbia Suicide Severity Rating Scale and engage the participant in risk management procedures based on their risk status.

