Study data that do not unblind investigators are accessible at all times for the PIs, the biostatistician, and all relevant Co-Is to review. The biostatistical team and study manager will conduct analyses of accrual, drop-outs, protocol deviations on a monthly basis initially, which may drop to quarterly once we are confident that procedures are functioning adequately. Drs. [name], [name], and [name] will review adverse events (AEs) and serious adverse events (SAEs) individually in real-time and in aggregate at each DSMB meeting (not less than annually). The PI ensures all protocol deviations, AEs, and SAEs are reported to the IRB and the NIMH program officer according to the applicable regulatory requirements.

For this study, the following standard AE definitions are used:

Adverse event: Any unfavorable and unintended sign or symptom temporally associated with the use of digital mental health interventions, regardless of whether it is considered related to intervention.

Serious Adverse Event: Any AE that results in any of the following outcomes:

- Death
- Life-threatening situation
- Event requiring inpatient hospitalization or prolongation of existing hospitalization
- Persistent or significant disability/incapacity

AEs are graded according to the following scale:

- Mild: An experience that is transient and requires no special treatment or intervention. The experience does not generally interfere with usual daily activities.
- Moderate: An experience that is alleviated with simple therapeutic treatments. The experience impacts usual daily activities.
- Severe: An experience that requires therapeutic intervention. The experience interrupts usual daily activities. If hospitalization (or prolongation of hospitalization) is required for treatment it becomes an SAE.

The study uses the following AE attribution scale:

- Not related: The AE is clearly not related to the study procedures (i.e., another cause of the event is most plausible and/or a clinically plausible temporal sequence is inconsistent with the onset of the event).
- Possibly related: An event that follows a reasonable temporal sequence from the initiation of study procedures, but that could readily have been produced by a number of other factors.
- Related: The AE is clearly related to the study procedures.

SAEs and specific treatment-associated AEs are reported to the IRB and NIMH program officer within 24 hours.

Data Safety Monitoring Board (DSMB)

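### Beyond suicidality screening, no enquiry for adverse events is described, and regular staff contact that could reveal them exists only in TES, so a by-arm comparison would be open to ascertainment bias

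*Protocol*

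**What the plan says.** The section on provisions to monitor safety defines an adverse event (AE) as "Any unfavorable and unintended sign or symptom temporally associated with the use of digital mental health interventions", whether or not it is thought to be caused by the intervention. Both arms use an app, so the definition applies to both. Inpatient hospitalization makes an event serious (SAE). The section gives severity grades and an attribution scale. The investigators are to "review adverse events (AEs) and serious adverse events (SAEs) individually in real-time and in aggregate at each DSMB meeting (not less than annually"). On reporting it says that "SAEs and specific treatment-associated AEs are reported to the IRB and NIMH program officer within 24 hours". It names no form, question or visit that brings an event to light.

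Table 2 of the participant timeline schedules a self-report survey at weeks 0, 4, 8 and 12, plus passive app-use tracking, for everyone. Table 1 lists the symptom and quality-of-life measures. The text after it says that "Additional data will be collected to evaluate intervention use, usability, satisfaction, and engagement" and adds discrimination and stigma measures. The survey packets are in the IRB system and not in the documents.

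On staff contact, the timeline says that "Participants will use the study apps and receive coaching (group 1 only) for the first 8 weeks", where group 1 is TES. Table 3 covers "Optional interview data to be collected from patients randomized to TES". The suicidality section lists automated PHQ-9 self-report first among its detection routes. It then adds detection "through direct communications with the study coach via phone or messaging", and feedback interviews.

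**The concern.** A reporting clock and an aggregate safety review work only on events that reach the study team. Suicidality has a screening pathway that does not depend on arm. A medical or psychiatric admission, an injury, or an accident while using the phone (phone distraction is what the protocol calls the main risk of the intervention) has no described enquiry in either arm. A TES participant has a coach for 8 weeks to whom such an event might be mentioned. A CT participant uses a self-guided app, with no scheduled staff contact described during follow-up.

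Two things are at stake. CT events can go unseen, which lowers the pooled count and means that no report is triggered. And if AEs or SAEs are tabulated by arm, a difference could reflect who had someone to tell.

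**Working it through.** The documents state no AE rate, detection rate or safety power, so there is no figure to reproduce. The check is mainly a comparison of routes by arm.

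**1. Routes by which an event could reach staff**

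| Route (protocol section) | TES | CT | Would it bring out a hospital stay or injury? |
|---|---|---|---|
| PHQ-9 item 9, follow-up item, alert, staff call (Protections Against Risk) | Yes | Yes | No; suicidality only |
| REDCap surveys, by phone if online is not feasible (Sub-aim 2.1 assessment; Table 2) | Yes | Yes | No such item described; packets not available |
| Coaching for 8 weeks (participant timeline) | Yes | No | Possibly, if mentioned |
| Optional coaching interview, week 4 | All invited | No | Possibly, if mentioned |
| Optional usability interviews, weeks 4, 6 and 8 | About 10 people | No | Possibly, if mentioned |
| Single-question survey on non-engagement | Yes | Yes | Only if it is the reason given |
| Documented reason for discontinuation | Yes | Yes | Only if it is the reason given |
| Post-trial focus group | About 12 people from both arms | | Not a safety enquiry |

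Ordinary Rush care continues in both arms, but no reporting from providers to the study is described. The planned Rush data exports are aggregated screening and referral counts, and the record review under Protected Health Information is for zip code only.

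**2. Illustration of size (all rates assumed)**

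Let p be the true 12-week AE risk, equal in both arms, qT and qC the shares of events detected in TES and CT, and nC the number in CT.

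- Apparent risk ratio, TES to CT = (p × qT)/(p × qC) = qT/qC. It does not depend on p or on arm sizes.
- CT events missed = nC × p × (1 − qC).
- Chance that no CT event is seen = (1 − p × qC)^nC.

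Take qT = 0.90 and p = 0.10. For nC use 65 (an assumed equal split of 130) and 50 (the CT number in the power paragraph).

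| qC | Apparent ratio | Missed, nC = 65 | Missed, nC = 50 |
|---|---|---|---|
| 0.90 | 1.00 | 65 × 0.10 × 0.10 = 0.65 | 0.5 |
| 0.70 | 0.90/0.70 = 1.29 | 65 × 0.10 × 0.30 = 1.95 | 1.5 |
| 0.50 | 0.90/0.50 = 1.80 | 65 × 0.10 × 0.50 = 3.25 | 2.5 |
| 0.30 | 0.90/0.30 = 3.00 | 65 × 0.10 × 0.70 = 4.55 | 3.5 |

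With a rarer event, p = 0.05 and qC = 0.30, the chance that no CT event is seen is (1 − 0.015)^65 = 0.37, or (1 − 0.015)^50 = 0.47. The first row shows that equal enquiry removes the distortion.

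**3. How strong the shared route is**

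The suicidality section says monitoring is weekly. Tables 1 and 2 give the PHQ-9 and the survey at weeks 0, 4, 8 and 12 only. The value of the one route common to both arms depends on which statement describes practice.

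**The case against.** A reader might infer that AEs are not asked about at all, and that only staff in contact with TES participants could hear of one. The documents do not support that. Item 9 screening, with its alert and call, is not limited to an arm, and it addresses the risk that the protocol calls most serious. The PHQ-9 and GAD-7 also measure worsening symptoms on the same schedule in both arms.

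A reader might also infer that the DSMB is shown a biased comparison between arms. The protocol speaks only of individual and aggregate review. The SAP lists suicidal ideation as a secondary outcome but plans no comparison of AEs or SAEs. The most that can be said is that such a comparison, if made, would be open to bias.

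Three further points stand. The unseen packets may contain an AE item. TES contact beyond coaching is modest, since the usability interviews go to about 10 people and the rest are offered one optional interview. And counts would be small: even 1 event against 4, with 65 per arm, gives a Fisher p-value of about 0.37.

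These points narrow the concern without removing it. Item 9 does not detect a hospital stay or an injury. Coaching is offered to the whole TES arm and to nobody in CT. Missed CT events matter for reporting and pooled review even if no by-arm table is ever made. And a protocol that specifies grading and attribution should also say how events are collected.

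**Conclusion.** The concern holds in limited form. Apart from item 9 suicidality screening in both arms, the documents describe no systematic AE or SAE enquiry, and the regular staff contact that might bring other events out is confined to TES. CT events can be missed, and a by-arm comparison would be open to ascertainment bias, probably making TES look worse.

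The size is unknown. The ratios of 1.29 to 3.00 rest on assumed detection shares and equal true risk, and show only that a moderate gap in detection could produce a noticeable apparent excess. The conclusion also depends on the survey packets containing no AE item. It concerns safety reporting and leaves the PHQ-9 and GAD-7 analyses untouched.

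**What to change.** - Check the survey packets. If they hold no such item, add a short identical set to the week 4, 8 and 12 REDCap surveys in both arms: new or worsened health problem, emergency visit, hospital stay. State this method and timing in the protocol. The items can reach only participants still in follow-up or yet to enrol. The section on Protected Health Information says about 114 participants had finished, which is 114/130 = 88% of the planned sample and leaves at most about 16.
- For all participants, record how each event became known. Build any by-arm AE/SAE table only from events ascertained the same way in both arms (solicited items and item 9 alerts). List events known only through coaching or interviews separately, flagged as TES-only ascertainment. This part still works for the whole sample.
- Reconcile the weekly suicidality monitoring in Protections Against Risk with the week 0, 4, 8 and 12 schedule in Tables 1 and 2.

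The cost is slightly longer surveys, more events to grade, an IRB amendment and one extra table or listing. No new visits are needed.
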